5.0 Statistical Methods

5.1 Software

The primary endpoint analyses will be performed using CRAN R Version 4.3.0 or higher using the boot package version 1.3-28.1 or above. Tables and listings will be produced using R and SAS version 9.4 (SAS Institute Inc.)

5.2 General Considerations

5.2.1 Listings

All study data will be included in the study data listings. Both the captured data and the MedDRA and WHO Drug codes will be provided. Listings will be displayed by subject in chronological order, if not stated otherwise.

Study data will be provided in electronic format, either as SAS XPT V5 files or CSV files.

5.2.2 Descriptive Statistics and Summary Tables

The total number of subjects in the study group (N) under the stated population will be displayed in the header of summary tables.

For age, height, weight, and BMI, the mean, standard deviation, minimum and maximum will be presented along with the n size from which the statistics were calculated.

PR and HR data will be presented as median, lower, and upper quartiles, min, max, and n size because they were not normally distributed in product development data (5.1.4).

For categorical variables, count, and percentage of subjects/counts in each device group and/or category will be presented. Percentages will be based on number of subjects with non-missing values, if not specified otherwise.

5.3 Endpoint Data Analysis Methods

5.3.1 Primary Endpoint

For the primary endpoint analysis, the ARMS will be calculated as the square root of the mean difference between the devices, as described in ISO 80601-2-61:2017(E). All PP subjects will be included in the primary endpoint analysis. The 95% CI for the primary endpoint analysis will be determined by jackknifing 100,000 samples with replacement and calculating a 95% CI from the distribution of ARMS among the jackknifed samples. If the ARMS and its upper 95% confidence interval are below the target of 3.0, the device will be determined to be non-inferior.

 INFORMED MINDSET MEDICAL	DOCUMENT VERSION: 3	THIS DOCUMENT SUPERSEDES VERSION: 2	PAGE: 12 OF 15
STATUS: Active	TITLE: Informed Vital Core - Statistical Analysis Plan	IDENTIFICATION: IVC-400-006d	
EFFECTIVE DATE: June 22, 2023	AUTHOR: [name]	APPROVED BY: [name]	

A Bland-Altman plot will be constructed from the differences vs. the average measured PRs and HRs for all PP subjects to assist in visualizing the differences between devices and the full range of PR and HR measurements. Since the differences were not normally distributed due to the “white coat” effect on PR in the product development data, upper and lower 95th percentiles will be drawn on the graph to aid in visualization rather than two standard deviations. Visible outliers with greater than +/- 6.0 BPM difference from the reference device will be tabulated. A threshold of +/- 6.0 BPM will be considered outlying because under a labelled ARMS of +/- 3.0, 95% of the differences should fall in the range of +/- 6.0 BPM against the reference.

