2.0 Study Objectives and Endpoints

2.1 Study Objective

The primary objective of the study is to establish that pulse rate (PR) measured with the IVC App are accurate to within +/- 3 BPM ARMS (average root mean square) of Heart Rate (HR) measured with the reference ECG device.

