2.1.1 Primary Endpoint

The primary endpoint is a non-inferiority comparison to an FDA approved reference device to establish that PR measured with the IVC App are accurate to an ARMS of +/- 3 BPM. In accordance with ISO 80601-2-61:2017(E) accuracy will be calculated as the RMS difference between the IVC App and the heart rate measured by the ECG reference device.

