3.0 Study Hypothesis

The IVC App can measure pulse rate between 50 and 130 BPM to an accuracy of +/-3 BPM average RMS. The hypothesis will be tested in a non-inferiority design. PR will be collected simultaneously with the IVC App and HR with an ECG reference device, and the ARMS and its 95% confidence interval calculated. If the upper limit of the 95% confidence interval of the ARMS is < 3.0, the IVC App will be determined to be non-inferior and the hypothesis that it is accurate to an ARMS of +/- 3.0 accepted.

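### SAP 5.3.1 omits the squaring from the formula for the primary statistic, which contradicts the RMS endpoint in 2.1.1 and the +/- 6.0 BPM rule in 5.3.1 itself.

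*Combined protocol and SAP*

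**What the plan says.** The analysis section, SAP 5.3.1, states: "the ARMS will be calculated as the square root of the mean difference between the devices, as described in ISO 80601-2-61:2017(E". The confidence interval in 5.3.1 comes from resampling that same statistic, and the device succeeds if the estimate and its upper 95% limit are below 3.0. Section 3.0 puts the test the same way: "If the upper limit of the 95% confidence interval of the ARMS is < 3.0".

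Elsewhere the SAP refers to a root mean square:

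- Section 2.1.1, citing the same ISO standard: "accuracy will be calculated as the RMS difference between the IVC App and the heart rate measured by the ECG reference device".
- Section 2.1: "accurate to within +/- 3 BPM ARMS (average root mean square".
- Section 3.0: "to an accuracy of +/-3 BPM average RMS".
- Section 6.2, Figure 2: the vertical axis is labelled as RMS.

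Section 5.3.1 also justifies its outlier threshold by saying that "under a labelled ARMS of +/- 3.0, 95% of the differences should fall in the range of +/- 6.0 BPM against the reference". No section prints a formula with squared differences.

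**The concern.** A root mean square is the square root of the mean of the squared differences. The sentence in 5.3.1 takes the root of the mean of the differences themselves. That is another statistic: positive and negative errors cancel, and its unit is the square root of BPM, while the limit is stated in BPM.

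This sentence is the only one in the SAP that sets out the calculation step for the number compared with 3.0. SAP 1.0 says that the SAP overrides the protocol's statistical text, and the readable part of the protocol gives no formula to fall back on. Someone programming from 5.3.1 would have to overrule it with 2.1.1, and no rule says that 2.1.1 takes precedence.

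**Working it through.** Let d be the difference, App PR minus ECG HR. This direction is an assumption, because 5.3.1 does not state one.

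**Inputs from the SAP**

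- Limit 3.0 (2.1, 3.0, 5.3.1).
- 95% of differences within +/- 6.0 at ARMS 3.0 (5.3.1).
- Per-protocol goal of 55 (6.2).
- Development ARMS of 0.9 for first sessions and 1.5 for worst-case sessions (6.2).

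The biases, the SDs paired with them and the normal distribution below are assumptions.

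**1. The plan's own 95% figure, RMS reading.** ARMS = sqrt(mean of d²). With zero bias this is the SD, so P(|d| <= 6) = 2Φ(6/3) - 1 = 95.4%. Holding the RMS at 3.0 with a bias of 1 to 2.5 BPM gives 95.5% to 98.3%. The stated 95% is reproduced.

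**2. The same figure, literal reading.** sqrt(mean d) = 3.0 means mean d = 3.0² = 9 BPM. The share within +/- 6.0 is then:

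| Assumed SD | Within +/- 6.0 |
|---|---|
| 1 | 0.1% |
| 1.5 | 2.3% |
| 3 | 15.9% |

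The literal wording cannot be squared with the outlier rule in the same section.

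**3. Effect on the limit.** A constant error of +8.5 BPM has a true ARMS of 8.5, but sqrt(8.5) = 2.92, which is below 3.0.

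**4. Pass rates at n = 55.** The simulation used 1,000 data sets with 2,000 resamples each. A pass needed both the estimate and the 97.5th percentile below 3.0. A literal pass was counted only if no resample mean was negative.

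| Bias, SD | True ARMS = sqrt(bias² + SD²) | Literal rule passes | RMS rule passes |
|---|---|---|---|
| +3, 1.5 | 3.35 | 100% | 0% |
| +5, 3 | 5.83 | 100% | 0% |
| +7, 3 | 7.62 | 99.8% | 0% |

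A separate run (500 data sets, 1,000 resamples) gave the same figures for the last two rows. The last row can be checked by hand. The standard error is 3/√55 = 0.405, and a pass needs a mean below 9 - 1.96 × 0.405 = 8.21. Then Φ((8.21 - 7)/0.405) is about 99.9%.

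**5. Unbiased device at the SAP's own ARMS.** With SD 0.9 the mean was negative, so its root was not real, in 50.4% of data sets; with SD 1.5, in 49.7%. At least one resample was undefined in 99.9% and 99.8%. The RMS rule passed 100% in both cases.

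**6. A wrong guess at the missing word.** A reader might repair the sentence with the mean absolute difference. Then 3.0 means a mean absolute difference of 9 BPM. That corresponds to an RMS of 9 × sqrt(π/2) = 11.3 under normality, with 40.5% within +/- 6.0. In simulation, an unbiased device with a true RMS of 8 passed in 96%.

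**The case against.** The strongest reply is that the slip is plain. The statistic is named ARMS, the abbreviation is expanded in the SAP, 2.1.1 says RMS difference, and the faulty sentence itself defers to the ISO standard. Sections 2.1 and 3.0 only name RMS without giving a calculation, so the explicit textual conflict is with 2.1.1 alone. This is right, and it settles the intent. It does not make the sentence correct.

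The hazard can also be called remote, for three reasons:

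- **Bias.** Mean bias cannot exceed RMS in size, so bias in the development data was at most 0.9 BPM, or 1.5 BPM for worst-case sessions. Nothing in the documents suggests +5 or +7 BPM. However, those data used a fingertip reference (SAP 6.1), so they do not bound bias against the ECG.
- **Visible failure.** For an unbiased device, or one that reads low, literal code would fail visibly. For one that reads consistently high it would run without warning.
- **Other outputs.** The Bland-Altman plot, the outlier table, the device summaries (4.2.4) and the supplied data would expose a large bias. At +5 with SD 3, about 37% of subjects would exceed +/- 6.0. None of these outputs enters the decision rule.

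Finally, the 95.4% assumes normal, unbiased differences, while the SAP reports that the differences were not normal. A rule of twice the statistic would suit any SD-like quantity. The check is therefore approximate, but the gap between 95% and at most 16% is too wide for that to matter.

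**Conclusion.** The concern holds. The calculation in 5.3.1 is wrong as written: it conflicts with 2.1.1 and with the outlier rule in its own section. This rests on the SAP text alone; the ISO standard was not consulted.

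The consequence depends on the sentence being programmed literally, and nothing in the documents shows that it was. In that case the limit becomes 9 BPM on mean bias, and the estimate is undefined about half the time for an unbiased device. The pass rates depend on the assumed biases, SDs and normality. No stated sample-size figure changes. It should be fixed because it concerns the formula that decides the trial.

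**What to change.** In SAP 5.3.1, define ARMS as the square root of the mean of the squared differences and print the formula over the n per-protocol subjects:

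ARMS = sqrt[(1/n) × Σ(IVC App PR - ECG HR)²]

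State that the 95% interval is obtained by resampling this same statistic. Sections 2.1, 2.1.1, 3.0 and 6.1 need no change.

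The adverse-event listing at the end of the combined file carries a run date of 21 November 2023, so programming has probably been done. The correction, for example in an SAP addendum, should therefore also confirm that the primary-endpoint code squared the differences.

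The cost is one sentence and one code check, with no effect on margin, data, enrolment or sample size.

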6.0 BACKGROUND, SAMPLE SIZE

6.1 Power Analysis Methodology

Power analysis and enrollment percentages for the PR measures were based on data collected from 571 consented subjects who attempted one or more simultaneous data collections from a Masimo MightySat fingertip PPG device (reference device) and the IVC App. The data collection rate across the 571 subjects was used to determine how many subjects to enroll in order to meet the target n size for the non-inferiority analysis. Collection success defined as a successful data collection from the IVC App was 80.5% (95% CI of 79% - 82%).

The measured PRs from both the reference device and the IVC App had a high kurtosis, as did the differences between devices. Data were also not Box-Cox normal, so they were treated as nonparametric. Deviation from a normal distribution has previously been observed in measured PR during studies and is attributed to a “white coat” phenomenon, with people who have higher 24-hour resting heart rates showing a more pronounced increase (1).

Under the assumption that the IVC App is non-inferior to the reference device, at 90% power the upper bound of the bootstrapped 95% CI should fall below 3.0, 90% of the time. Subsampling the differences between the devices at systematically varied n sizes and calculating an ARMS and its 95% CI on each subsample gives a distribution of 95% confidence intervals for each n size. The distribution of confidence

 INFORMED MINDSET MEDICAL	DOCUMENT VERSION: 3	THIS DOCUMENT SUPERSEDES VERSION: 2	PAGE: 13 OF 15
STATUS: Active	TITLE: Informed Vital Core - Statistical Analysis Plan	IDENTIFICATION: IVC-400-006d	
EFFECTIVE DATE: June 22, 2023	AUTHOR: [name]	APPROVED BY: [name]	

intervals is used to determine power at that n size. Since the distribution of differences was nonparametric, 95% CI distributions were bagged (bootstrap aggregated). The bagging procedure was performed as follows:

1. A cohort of 475 or 484 subjects with one paired PR measurement each was established as described later.
2. Random subsamples with replacement were selected from the cohort at n sizes from 20 to 100 in intervals of 5. For each n size, 4,000 subsamples were generated.
3. The 95% confidence interval on the Arms was bootstrapped on each subsample by jackknifing with replacement 2,000 times.
4. The 95% confidence interval upper bounds were aggregated for each n size to produce a distribution of upper 95% confidence intervals.

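### At n = 55 the bootstrap upper limit that decides the trial is too low: about 6-7% false acceptance at a true ARMS of 3.0 with normal differences, against the 2.5% implied, and only power is checked

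*Combined protocol and SAP*

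**What the plan says.** The endpoint is a root mean square: SAP 2.1.1 states that "accuracy will be calculated as the RMS difference between the IVC App and the heart rate measured by the ECG reference device". SAP 3.0 gives the decision rule: "If the upper limit of the 95% confidence interval of the ARMS is < 3.0, the IVC App will be determined to be non-inferior". SAP 5.3.1 repeats it ("If the ARMS and its upper 95% confidence interval are below the target of 3.0") and builds the interval by "jackknifing 100,000 samples with replacement and calculating a 95% CI from the distribution of ARMS among the jackknifed samples". SAP 5.1 has the primary analysis run in R "using the boot package version 1.3-28.1 or above". No section names the bootstrap interval type or states an alpha.

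SAP 6.1 evaluates the rule as follows: "Under the assumption that the IVC App is non-inferior to the reference device, at 90% power the upper bound" of the interval should fall below 3.0 in 90% of cases. In that simulation, "The 95% confidence interval on the Arms was bootstrapped on each subsample by jackknifing with replacement 2,000 times". SAP 6.2 applies it to two development cohorts: 475 first sessions (ARMS 0.9) and 484 worst sessions (ARMS 1.5). The second shows 90% power at 40 subjects and 95% at 45, and it sets the per-protocol goal of 55. SAP 6.1 also reports that the differences had high kurtosis and were not Box-Cox normal, and that the development reference was a fingertip PPG device.

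**The concern.** The whole claim rests on one upper limit being below 3.0. The sampling distribution of a mean square is right-skewed, and its estimated spread moves with its estimated size. A sample that happens to contain few large differences gives both a low ARMS and a narrow bootstrap distribution. Those are the samples in which a borderline device passes, so simple bootstrap limits sit too low at moderate n.

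A reader who sees a 95% upper limit below 3.0 will assume that a device at 3.0 had a 2.5% chance of passing. If the chance is several times larger, the limit does not carry its label. A power-only check cannot show this, and it even favours the fault, because a limit that is too low raises apparent power.

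**Working it through.** **Inputs.** Limit 3.0 (SAP 3.0, 5.3.1). Upper end of a two-sided 95% interval, hence 2.5% in the relevant tail (the natural reading of SAP 3.0). Percentile type (the natural reading of SAP 5.3.1, which takes the interval from the distribution of resampled ARMS). n = 55 (SAP 6.2). ARMS = sqrt(mean of d²), following SAP 2.1.1. The development differences are not in the documents, so their shape has to be assumed.

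**1. The plan's own power figure.** It cannot be reproduced exactly without the 484 differences, but it can be compared with assumed shapes. At ARMS 1.5 and n = 40, with the percentile limit, normal differences give 100% power, t4 about 96%, and a normal with 10% contamination at 4 times the SD about 93%. The plan states 90%. The worst-session tails are therefore at least as heavy as the heaviest of these shapes.

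**2. Hand check, normal differences, true ARMS 3.0.** The sum of d²/9 is chi-square with 55 df.
- Exact 2.5% rule: the 2.5% point of chi-square(55) is 36.40, so the observed ARMS must be below 3 × sqrt(36.40/55) = 2.44.
- Symmetric rule: the relative SE of ARMS is sqrt(2/(4 × 55)) = 0.0953. The rule ARMS × (1 + 1.96 × 0.0953) < 3 accepts below 3/1.187 = 2.53. Then P(chi-square(55) < 55 × (2.53/3)²) = P(chi-square(55) < 39.0) ≈ 5%.

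So a symmetric limit with a known relative SE already doubles 2.5%. Estimating the spread from 55 values adds to this.

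**3. Simulation of the rule.** Draw 55 differences scaled to ARMS 3.0, resample subjects with replacement, and accept if the upper limit is below 3.0 (6,000 trials × 1,000 resamples, Monte Carlo SE about 0.3-0.6 points).

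| Differences | Percentile | Basic | BCa |
|---|---|---|---|
| Normal | 6.0% | 5.4% | 3.8% |
| Laplace (assumed) | 11.5% | 10.9% | 7.4% |
| t5 (assumed) | 14.1% | 13.7% | 9.9% |
| t4 (assumed) | 17.7% | 17.5% | 12.6% |
| 10% contamination at 4 × SD (assumed) | 20.7% | 21.7% | 14.8% |

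Repeat runs of the normal case gave 6.0-6.8% for percentile (6.7% with 20,000 trials) and 3.8-4.6% for BCa. Rounding differences to integers changes little (6.8%). At n = 68 (85 × 0.805 = 68.4, before other losses) the normal case is 5.6% for percentile and 3.8% for BCa.

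**4. Where the error reaches 2.5%.** With the percentile limit and normal differences, this is at a true ARMS of about 3.14 (simulated acceptance there 2.6-2.8%). At 3.5 it is about 0.2%.

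**5. Why 11-21% is not a bound.** Two invented cohorts of 484 were tuned roughly to the plan's power: five outliers of 9 BPM give 91%/93%/95% at n = 40/45/55, and ten of 8 BPM give 91%/93%/96%. Doubled to ARMS 3.0, they give about 43% and 32% false acceptance at n = 55. They only show that tails consistent with SAP 6.2 can lie outside the range in the table.

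**6. Power at ARMS 1.5, n = 55** (normal/Laplace/t5/t4/contaminated): percentile 100/99.5/98.4/96.5/95.8%; BCa 100/97.7/95.5/92.6/86.5%. At ARMS 0.9, BCa power is 99.1% or more for every shape.

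**The case against.** - **The device is nowhere near 3.0.** Development ARMS was 0.9, and 1.5 in the worst sessions; for normal differences the shift is only 0.14 BPM. This stands as a limit on practical effect. It is reassurance and not proof, because those values were measured against a fingertip PPG device and the trial uses ECG.
- **The plan states no alpha.** True: 2.5% is inferred from the two-sided 95% interval. On a one-sided 95% reading the normal-case percentile figure is 9.3-10.0% against 5%, so the limit is too low either way.
- **The wording is clear enough.** This stands. A reader might infer that calling the procedure a jackknife, or leaving type and sidedness unnamed, makes the rule undefined or causes the excess error. The documents do not support that. Resampling with replacement, the word bootstrapped in SAP 6.1 and the boot package all point to a bootstrap. SAP 3.0 describes the upper limit of an ordinary 95% interval. The looser wording in SAP 6.1 ("to produce a distribution of upper 95% confidence intervals") does not change this. The excess is a small-sample property of the limit itself.
- **BCa is no cure and costs power.** Also true. It reduces the excess without removing it, so the actual error rate must be reported as well.

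**Conclusion.** The point holds. On the natural reading, at n = 55, the rule accepts a device at a true ARMS of 3.0 in about 6-7% of trials with normal differences, against 2.5% implied. Normal differences are the mild case, given the kurtosis that SAP 6.1 reports. The larger figures rest on assumed shapes. A reader might take 11-21% (or the 32-43% of the tuned cohorts) as this trial's error rate, or conclude that a positive result would be unsafe. Neither follows: the documents give no kurtosis value, the tails against ECG are unknown, and at an ARMS of 0.9-1.5 the decision would seldom change. The fault is that the limit lacks its nominal coverage at the boundary and that SAP 6.1-6.2 never test the rule there.

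**What to change.** 1. In SAP 5.3.1 and 6.1, specify the BCa upper limit of a two-sided 95% bootstrap interval, resampling per-protocol subjects, from the boot package already named in SAP 5.1. Normal-case false acceptance falls to about 4-5%.
2. Before database lock, rescale the 475 first-session differences to ARMS 3.0 (factor 3.0/0.9 = 3.3), with the 484 worst-session differences as sensitivity (factor 3.0/1.5 = 2). Apply the exact rule at n = 55. Report the simulated false-acceptance rate in the SAP and beside the primary result, and do not leave 2.5% implied. Note that tails against ECG may differ and that rescaling assumes an unchanged shape.
3. Restate the SAP 6.2 power for the rule used.
4. Replace jackknifing with bootstrap throughout. This is a wording correction only.

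**Cost.** SAP text and a rerun of the existing simulation on data in hand; no new subjects. The real price is power at the 1.5 BPM worst case, which under BCa may fall below the stated 95% (about 93% for t4 and 87% for the contaminated shape, both assumed). At 0.9 BPM it stays at about 99% or more. Full calibration is not requested: even at a nominal 99.9% upper level, BCa leaves 3.7% for t4 and 9.4% for the contaminated shape.

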5.3.2 IVC App PR Reporting Rate

The overall PR reporting rate of the IVC App will be calculated from the ITC population. All subjects with an IVC App PR from the first non-fallback session will be counted as IVC App collections. The total count of subjects with IVC App collections will be divided by the count of subjects in the ITC group to calculate the overall PR reporting rate for the IVC App.

A second rate will be calculated as above, only excluding subjects who had no IVC App sessions collected due to repeated technical failures. The second rate reflects the proportion of subjects who were able to use the IVC App and is more reflective of proportion of sessions where a reliable PR can be determined from the analyzed video frames. The number of subjects excluded due to technical failures will also be reported.

6.0 BACKGROUND, SAMPLE SIZE

6.1 Power Analysis Methodology

Power analysis and enrollment percentages for the PR measures were based on data collected from 571 consented subjects who attempted one or more simultaneous data collections from a Masimo MightySat fingertip PPG device (reference device) and the IVC App. The data collection rate across the 571 subjects was used to determine how many subjects to enroll in order to meet the target n size for the non-inferiority analysis. Collection success defined as a successful data collection from the IVC App was 80.5% (95% CI of 79% - 82%).

The measured PRs from both the reference device and the IVC App had a high kurtosis, as did the differences between devices. Data were also not Box-Cox normal, so they were treated as nonparametric. Deviation from a normal distribution has previously been observed in measured PR during studies and is attributed to a “white coat” phenomenon, with people who have higher 24-hour resting heart rates showing a more pronounced increase (1).

Under the assumption that the IVC App is non-inferior to the reference device, at 90% power the upper bound of the bootstrapped 95% CI should fall below 3.0, 90% of the time. Subsampling the differences between the devices at systematically varied n sizes and calculating an ARMS and its 95% CI on each subsample gives a distribution of 95% confidence intervals for each n size. The distribution of confidence

 INFORMED MINDSET MEDICAL	DOCUMENT VERSION: 3	THIS DOCUMENT SUPERSEDES VERSION: 2	PAGE: 13 OF 15
STATUS: Active	TITLE: Informed Vital Core - Statistical Analysis Plan	IDENTIFICATION: IVC-400-006d	
EFFECTIVE DATE: June 22, 2023	AUTHOR: [name]	APPROVED BY: [name]	

intervals is used to determine power at that n size. Since the distribution of differences was nonparametric, 95% CI distributions were bagged (bootstrap aggregated). The bagging procedure was performed as follows:

1. A cohort of 475 or 484 subjects with one paired PR measurement each was established as described later.
2. Random subsamples with replacement were selected from the cohort at n sizes from 20 to 100 in intervals of 5. For each n size, 4,000 subsamples were generated.
3. The 95% confidence interval on the Arms was bootstrapped on each subsample by jackknifing with replacement 2,000 times.
4. The 95% confidence interval upper bounds were aggregated for each n size to produce a distribution of upper 95% confidence intervals.
5. 90th and 95th percentiles were calculated to find the power at each n size.

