6.2 Power Analysis for Sample Size

A total of 85 subjects (n = 85) will be enrolled.

[figure not shown]

Figure 1. Power analysis workflow. The first sessions were selected as representative of the study design for the initial power analysis (left). A second set of sessions with the largest difference from the reference device were used in a conservative scenario (right).

A total of 475 subjects out of the 571 in the product development cohort had data collected the IVC App in from the first PR collection and were included in the initial power analysis. Only the first PR sessions were used in order to accurately model the clinical study design, where subjects will have only one IVC App collection. The overall ARMS was 0.9 BPM. The bagging procedure was performed on n sizes ranging from 20 to 100 subjects (Figure 2). At all n sizes in the analysis, the 95th percentile of the confidence intervals was below the target ARMS of 3.0. Thus, n sizes of 20 or greater are powered at 95%.

 INFORMED MINDSET MEDICAL	DOCUMENT VERSION: 3	THIS DOCUMENT SUPERSEDES VERSION: 2	PAGE: 14 OF 15
STATUS: Active	TITLE: Informed Vital Core - Statistical Analysis Plan	IDENTIFICATION: IVC-400-006d	
EFFECTIVE DATE: June 22, 2023	AUTHOR: [name]	APPROVED BY: [name]	

Bootstrapped power

[figure not shown]

Figure 2. Bagging results for sample sizes ranging from 20 to 100. The filled-in squares show the 95th percentile and the open circles show the 90th percentile of the upper bound of the confidence intervals. The x-axis shows the sample size of the subsamples and the y-axis is the RMS. All 95th percentiles are below the target ARMS of 3.0.

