As well as the first IVC App collection attempt used in the power analysis above, some of the subjects provided additional data collection sessions under varied conditions for product development. To perform a more conservative power analysis, the session with the largest absolute difference from the reference device was selected for each subject. The same bagging analysis over 484 “worst case” collections with an ARMS of 1.5 BPM showed 90% power with 40 subjects and 95% power with 45 subjects. The conservative power analysis was used to establish a PP group goal of 55 subjects to ensure that power is at or above 95%. Additionally, a sample size greater than 50 subjects ensures that the sample is likely to be representative of the IVC App performance under the Central Limit Theorem. Since the IVC App is designed to report only reliable results and inform the user that a PR could not be collected otherwise, not all sessions result in a successful PR measurement. As mentioned above, the PR collection rate for the IVC app was 80%, so the study will be overenrolled to reach the target PP group size. A total of 85 subjects will be enrolled, allowing for screening failures, withdrawals, technical failures, and sessions where the IVC App does not report a PR.

In order to ensure a diverse PP group, the enrollment target for the PP group is 15% in the dark (Fitzpatrick 5-6) skin tone group. Initially enrollment will be random, but targeted enrollment may be used to meet skin tone goals if the dark skin tone PP group is projected to fall below the 15% goal.

 INFORMED MINDSET MEDICAL	DOCUMENT VERSION: 3	THIS DOCUMENT SUPERSEDES VERSION: 2	PAGE: 15 OF 15
STATUS: Active	TITLE: Informed Vital Core - Statistical Analysis Plan	IDENTIFICATION: IVC-400-006d	
EFFECTIVE DATE: June 22, 2023	AUTHOR: [name]	APPROVED BY: [name]	

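### Does the too-narrow confidence interval around the 80.5% collection rate undermine the enrolment of 85?

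*Combined protocol and SAP*

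**What the plan says.** SAP section 6.1 describes development data on "data collected from 571 consented subjects who attempted one or more simultaneous data collections" with the app and a fingertip reference device. It then says: "The data collection rate across the 571 subjects was used to determine how many subjects to enroll". Success is counted on the app alone ("Collection success defined as a successful data collection from the IVC App"), and the rate "was 80.5% (95% CI of 79% - 82"%). The section does not say whether the unit is the subject or the session.

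Section 6.2 gives subject counts from the same cohort. The initial power analysis used first sessions: "A total of 475 subjects out of the 571 in the product development cohort had data collected the IVC App" at the first collection. The conservative power analysis used each subject's worst session: "The same bagging analysis over 484 “worst case” collections with an ARMS of 1.5 BPM". The same section notes that some subjects gave extra sessions under varied conditions.

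For enrolment, section 6.2 states that "the PR collection rate for the IVC app was 80%, so the study will be overenrolled to reach the target PP group size". The per-protocol goal is 55 and enrolment is 85. The margin is meant to cover screening failures, withdrawals, technical failures and sessions in which the app reports no pulse rate.

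**The concern.** The printed interval is only 3 points wide, which is too narrow for a proportion near 80% estimated on 571 people. The point estimate also disagrees with the 475 of 571 in the next section. Section 6.1 names this rate as the basis for the number enrolled. If the rate were too high, or much less certain than stated, 85 enrolled might yield fewer than the 55 per-protocol subjects the SAP wants, and power for the primary test could fall below the level claimed. The rate also covers app failures only, while section 4.1.3 says that the ECG reference sometimes gives an unusable strip.

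**Working it through.** **Inputs.** Cohort 571, rate 80.5%, printed limits 79% and 82% (section 6.1). First-session count 475, worst-case count 484, per-protocol goal 55, enrolment 85, and worst-case power of 90% at 40 subjects and 95% at 45 (section 6.2).

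**1. Trying to reproduce the printed interval.**
- SE = √(0.805 × 0.195 / 571) = 0.0166.
- 95% limits = 0.805 ± 1.96 × 0.0166 = 77.3% to 83.7%. Wilson and Clopper-Pearson limits for 460/571 are 77.1% to 83.6% and 77.1% to 83.7%.
- The printed half-width is 1.5 points, and 0.015 / 0.0166 = 0.905 SE, which is about a 63% interval at n = 571.
- As a 95% interval it needs n = 0.805 × 0.195 × (1.96 / 0.015)² ≈ 2,680 independent observations. Rounding of the limits allows half-widths from 2 points down to 1 point, or about 1,510 to 6,030.

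So the interval is not reproduced with 571 subjects.

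**2. Is 80.5% a subject-level rate at all?**
- 459/571 = 80.4% and 460/571 = 80.6%. No whole count out of 571 rounds to 80.5%.
- 475/571 = 83.2% (Wilson 79.9% to 86.0%), and 484/571 = 84.8%.
- If 475 subjects already had app data at their first collection, a per-subject success rate in this cohort cannot be below 83.2%.

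A rate over sessions fits both the value and the width: 2,680 / 571 is about 4.7 sessions per subject, and 1,510 / 571 is about 2.6. This is an inference, because the session count is not in the readable text.

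**3. What the sizing uses.** Enrolment needed for 55 per-protocol subjects, counting app failures only, is 55 / rate:
- at 80.5%: 68.3, so 69
- at 83.2%: 66.1, so 67
- at 77.2% (about the lower limit in step 1): 71.2, so 72

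All are below 85. The loss from other causes that still leaves an expected 55 is 1 − 55 / (85 × 0.805) = 19.6% at 80.5%, and 1 − 55 / (85 × 0.832) = 22.2% at 83.2%.

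**4. Chance of reaching the goal.** The SAP does not quantify other losses, so I assume a loss L of 10%, 15% or 20% and take the per-protocol count as binomial with 85 trials and probability rate × (1 − L).

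| Rate | L | P(≥ 55) | P(≥ 45) |
|---|---|---|---|
| 77.2% | 10% | 86% | > 99.9% |
| 77.2% | 15% | 62% | 99.4% |
| 77.2% | 20% | 33% | 96.2% |
| 80.5% | 10% | 95% | > 99.9% |
| 80.5% | 15% | 80% | 99.9% |
| 80.5% | 20% | 53% | 98.9% |
| 83.2% | 10% | 99% | > 99.9% |
| 83.2% | 15% | 91% | > 99.9% |
| 83.2% | 20% | 69% | 99.7% |

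The goal of 55 already sits 10 subjects above the 45 at which the SAP reports 95% power in its worst-case scenario. Falling short of 55 is therefore not the same as losing the stated power.

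**The case for a change.** The best argument for a correction is that the mismatch can be shown from the SAP alone and costs only wording to repair. Rounding does not explain the interval. If 80.5% is a session rate, its denominator is missing and an interval that narrow probably treats repeated sessions on one person as independent. The trial counts subjects at a single session (sections 5.3.2 and 6.2), so the matching development figure is 475/571. The step from 55 to 85 cannot be reproduced either, because losses other than app non-reporting are not given numbers. The table shows that those losses matter more to reaching 55 than the rate does.

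Most of this stands as description: the unit is unlabelled and the interval does not fit the cohort named. Three things limit it.

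- A session-level rate under another label is not a wrong rate. Figure 1 of the SAP, the workflow for selecting sessions, is not reproduced in the text available here and may give the counts.
- The 475 may have required a paired fingertip reading, since the cohorts in section 6.1 are described as paired, while 80.5% is defined on the app alone. That would make 83.2% a floor for the app's first-session rate, which strengthens the view that 80% is cautious.
- ECG losses are not ignored. Section 4.1.3 plans two sessions per subject and up to three fallback sessions, and section 6.2 names technical failures among the losses that 85 must cover.

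**Conclusion.** The arithmetic criticism is right and the consequence is nil. The 79% to 82% interval does not belong to 571 subjects, and 80.5% is not the subject-level rate, but the interval is background and feeds no calculation. The value that does feed the sizing, 80%, is below the SAP's own 83.2%, and substituting the latter would lower the requirement by two subjects (69 to 67) against 85 planned. Relabelling the rate would change neither the number enrolled nor the stated power, and it leaves the primary analysis and its decision rule as they are.

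This rests on two assumptions. The first is that other losses are of the order of 10% to 20%, for which the documents give no figure. At the pessimistic corner of that range (77.2% and 20%), the chance of at least 45 per-protocol subjects is still 96.2%. The second is that the SAP's power figures at 40 and 45 subjects are taken as printed, since the development data are not available to rerun them. A reader of the study report should treat 79% to 82% as a labelling slip and use 475/571 as the subject-level benchmark for the app's reporting rate.
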